#### **5.4.1 Primary Efficacy Assessment**

The primary endpoint is objective response rate (ORR) in the platinum refractory subgroup (See [Section 8.3.1](#) for the definitions of ORR). All randomized subjects will be monitored by radiographic assessment on an every 6 week schedule every 6 weeks ( $\pm 7$  days) from first dose for the first 12 months (until week 48) and every 12 weeks ( $\pm 7$  days) thereafter (beginning from the first on-study assessment on week 6 [ $\pm 7$  days]), to determine changes in tumor size. RECIST 1.1 criteria will be used for the assessment. For details regarding the response criteria using RECIST 1.1 refer to [Appendix 3](#).

#### **5.4.2 Secondary Efficacy Assessment**

The secondary endpoint of ORR in platinum eligible subgroup is defined similarly as described for the primary endpoint.

The BICR-assessed PFS is defined as the time from randomization to the date of first documented disease progression, as assessed by the BICR using RECIST 1.1 criteria, or death due to any cause, whichever occurs first. Subjects who died without a reported progression will be considered to have progressed on the date of their death. Subjects who did not progress or die will be censored on the date of their last evaluable tumor assessment. Subjects who did not have any on study tumor assessments and did not die will be censored on the date they were randomized. Subjects who started any subsequent anti-cancer therapy, including tumor-directed radiotherapy and tumor-directed surgery, without a prior reported progression will be censored at the last evaluable tumor assessment prior to/on initiation of the subsequent anti-cancer therapy.

Every effort will be made to collect survival data on all randomized subjects including subjects withdrawn from treatment for any reason, who are eligible to participate in the study and who have not withdrawn consent for survival data collection. If the death of a subject is not reported, all dates in this study representing a date of subject contact will be used in determination of the subject's last known date alive.

PD-L1 expression is defined as the percent of tumor cell membrane staining in a minimum of 100 evaluable tumor cells per validated Dako PD-L1 IHC assay.

Analysis of the secondary endpoints will be performed at the same time as the primary endpoint analysis.

To determine changes in tumor size, RECIST 1.1 criteria will be used for the assessment. For details regarding response criteria using RECIST 1.1 refer to [Appendix 3](#).

[REDACTED]

[REDACTED]

[REDACTED]

[REDACTED]

[REDACTED]

[REDACTED]

[REDACTED]

[REDACTED]

[REDACTED]

[REDACTED]

[REDACTED]

[REDACTED]

[REDACTED]

[REDACTED]

[REDACTED]

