### 3. INVESTIGATIONAL PLAN

#### 3.1 Study Subgroups

CA209714 will recruit patients with recurrent or metastatic first line SCCHN.

Subjects must have metastatic or recurrent disease that is not amenable to therapy with curative intent (surgery or radiation therapy with or without chemotherapy). Subjects that refuse potentially curative salvage surgery for recurrent disease are ineligible.

Two subgroups will be enrolled into this study. Subjects will be classified as platinum refractory or platinum eligible:

- **Platinum refractory subgroup (n = approximately 216):** subjects with histologically confirmed SCCHN that has recurred during or less than 6 months after completion of previous platinum-based chemotherapy, given as adjuvant or neoadjuvant treatment or as part of multimodal treatment (chemotherapy, surgery, radiotherapy) for locally advanced disease. Subjects should have not received systemic anti-cancer therapy in the recurrent or metastatic setting.
- **Platinum eligible subgroup (n = approximately 180):** subjects with histologically confirmed SCCHN who are platinum naive, or have recurred 6 months or more after completion of previous platinum-based chemotherapy, given as adjuvant or neoadjuvant treatment or as part of multimodal treatment (chemotherapy, surgery, radiotherapy) for locally advanced disease. Subjects should have not received systemic anti-cancer therapy in the recurrent or metastatic setting.

Enrollment to each cohort will close when the predetermined number of patients in each cohort has been reached. If one cohort closes recruitment as it has reached the predefined number of patients in that particular subgroup (216 or 180), enrollment of patients into the other subgroup will remain open until it has completed enrollment.

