Tumor progression or response endpoints will be assessed using Response Evaluation Criteria In Solid Tumors (RECIST 1.1) criteria. Treatment with study medication will continue until RECIST 1.1 defined progression, unacceptable toxicity, 24 months of treatment, or withdrawal of consent. See [Section 3.6](#) for full details of discontinuation of study drug treatment.

Dose reductions will not be allowed for nivolumab, ipilimumab, or ipilimumab-placebo. Treatment beyond initial investigator-assessed progression (either clinical or radiographical) is permitted for nivolumab and ipilimumab or ipilimumab-placebo up to a maximum of 24 months from date of first dose if the subject has an investigator-assessed clinical benefit and is tolerating study drug (see [Section 4.5.6.1](#)).

A Data Monitoring Committee (DMC) will be established and meet regularly during the study to ensure that subject safety is carefully monitored and to provide oversight regarding safety and efficacy considerations in protocol CA209714, see [Section 7](#).

The ORR analyses for each of the platinum eligible and platinum refractory subgroups will be conducted when the sufficient number of randomized subjects in that subgroup have been followed at least 9 months. The accrual duration will be approximately 13 months. Survival follow-up may continue for up to 5 years from the time of this analysis. The study will end once survival follow-up has concluded.

The study design schematic is presented in [Figure 3.2-1](#).

This study will consist of three phases: screening, treatment, and follow-up.

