## 8.3 Endpoints

### 8.3.1 Primary Endpoint(s)

The primary objective in the study will be measured by the primary endpoint of ORR in Platinum Refractory subgroup. ORR is defined as the number of subjects with a best overall response (BOR) of a complete response (CR) or partial response (PR) divided by the number of randomized subjects for each treatment group. The BOR is defined as the best response designation, as determined by BICR, recorded between the date of randomization and the date of progression, as

assessed by BICR per RECIST 1.1 or the date of subsequent anticancer therapy (including tumor-directed radiotherapy and tumor-directed surgery), whichever occurs first. For subjects without evidence of RECIST 1.1 progression or subsequent anticancer therapy, all available response designations will contribute to the BOR assessment. For subjects who continue treatment beyond progression, the BOR will be determined based on response designations up to the time of initial RECIST 1.1 progression.

ORR will be further characterized by Duration of Response (DOR) and Time to Response (TTR). DOR is defined as the time between the date of first confirmed response to the date of the first documented tumor progression (per RECIST 1.1), or death due to any cause, whichever occurs first. Subjects who neither progress nor die will be censored on the date of their last evaluable tumor assessment. Subjects who started any subsequent anti-cancer therapy without a prior reported progression will be censored at the last evaluable tumor assessment prior to or on initiation of the subsequent anti-cancer therapy. TTR is defined as the time from randomization to the date of the first confirmed CR or PR. DOR and TTR will be evaluated for responders (confirmed CR or PR) only.

The final analysis of the primary endpoint will occur at least 9 months after the last subject in the platinum refractory subgroup has been randomized.

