### **8.3.2 Secondary Endpoint(s)**

The secondary endpoint of ORR and DOR in platinum eligible subgroup is defined similarly as described for the primary endpoint.

The BICR-assessed PFS is defined as the time from randomization to the date of first documented disease progression, as assessed by the BICR using RECIST 1.1 criteria, or death due to any cause, whichever occurs first. Subjects who died without a reported progression will be considered to have progressed on the date of their death. Subjects who did not progress or die will be censored on the date of their last evaluable tumor assessment. Subjects who did not have any on study tumor assessments and did not die will be censored on the date they were randomized. Subjects who started any subsequent anti-cancer therapy, including tumor-directed radiotherapy and tumor-directed surgery, without a prior reported progression will be censored at the last evaluable tumor assessment prior to/on initiation of the subsequent anti-cancer therapy.

OS is defined as the time between the date of randomization and the date of death. For subjects without documentation of death, OS will be censored on the last date the subject was known to be alive.

PD-L1 expression is defined as the percent of tumor cell membrane staining in a minimum of 100 evaluable tumor cells per validated Dako PD-L1 IHC assay.

The final analysis of the ORR in each of platinum eligible and platinum refractory subgroups will occur at least 9 months after the sufficient number of subjects in that subgroup have been randomized (approximately 180 in platinum eligible and 216 in platinum refractory subgroups). Analysis of the PFS and OS will also be performed at the same time as the ORR analysis.

[REDACTED]

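### Two protocol places tie every secondary endpoint to the platinum refractory analysis date, while other sections give the platinum eligible cohort its own follow-up clock

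*Protocol*

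**What the plan says.** **Rule A: one date for everything.** Protocol 5.4.2 and the Synopsis (Secondary Endpoints) carry the same sentence: "Analysis of the secondary endpoints will be performed at the same time as the primary endpoint analysis". Section 5.4.1 fixes what the primary endpoint is: "The primary endpoint is objective response rate (ORR) in the platinum refractory subgroup". Section 8.3.1 sets its final analysis "at least 9 months after the last subject in the platinum refractory subgroup has been randomized". Section 5.4.2 itself names platinum eligible ORR as a secondary endpoint: "The secondary endpoint of ORR in platinum eligible subgroup is defined similarly as described for the primary endpoint".

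**Rule B: a clock for each cohort.** Protocol 8.3.2 says that the final ORR analysis in each subgroup "will occur at least 9 months after the sufficient number of subjects in that subgroup have been randomized", giving about 180 platinum eligible and 216 platinum refractory, and places PFS and OS at the same time as the ORR analysis. Section 3.2 times each subgroup's ORR analysis "when the sufficient number of randomized subjects in that subgroup have been followed at least 9 months". The Synopsis design text says much the same, so the Synopsis holds both rules. SAP 2.1 also uses a clock for each subgroup, but at 6 months after its last randomized subject.

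**Enrolment.** Section 3.1 closes each cohort at its own target. If one fills first, "enrollment of patients into the other subgroup will remain open until it has completed enrollment". No closing date per cohort is given. The only accrual figure, about 13 months in Section 3.2, is for the study and names no cohort.

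**The concern.** Under Rule A, the platinum eligible results are cut on a date set by the other cohort's enrolment. If platinum eligible is the slower cohort, its last entrants have less than the 9 months that Rule B gives them.

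ORR divides by all randomized subjects (Protocol 8.3.1) and needs a confirmed response (SAP 4.1.1). A late entrant who will respond but is not yet confirmed therefore counts as a non-responder, and the estimate falls. DOR, PFS and OS are handled by censoring, so short follow-up there mainly costs precision and landmark rates.

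The pooled objectives in Section 1.5.2 are also affected. Rule A puts them on the refractory date. Rule B refers to the ORR analysis, of which there are two, and does not say which one the pooled results follow.

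**Working it through.** **1. Figures in the plan that do not depend on the timing sentence.** The stated 84% power (144 v 72, ORR 35% v 15%, two-sided 0.05) reproduces with a Wald test on the log odds ratio: 84.8% at a single look and 84.3% with the one-interim boundary. The exact intervals for N=120 in Table 8.1-1 also reproduce. None of these uses the analysis date of the platinum eligible cohort.

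**2. Minimum follow-up.** Let platinum refractory reach its target at time T and platinum eligible at T + L. The earliest primary analysis is T + 9 (Protocol 8.3.1). Minimum platinum eligible follow-up is then:

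- Rule A at that earliest date: (T + 9) − (T + L) = 9 − L months.
- Rule B: at least 9 months, whatever L is.

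**3. Landmark rates.** SAP 7.5.3.1 plans PFS rates at 3, 6, 12 and 24 months, and SAP 7.5.4.1 plans OS rates at 6, 9, 12 months and later. Each is produced only if minimum follow-up reaches the time point. SAP 7.5.4.4 measures minimum follow-up from the last patient's randomization to the cutoff. I apply it within the cohort, because these analyses are done by cohort.

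| L (months) | Minimum follow-up, 9 − L | Rates lost relative to Rule B |
|---|---|---|
| 0 | 9 | none |
| 1 | 8 | OS at 9 months |
| 3 | 6 | OS at 9 months |
| 4 | 5 | OS at 9 and 6 months, PFS at 6 months |
| 6 | 3 | OS at 9 and 6 months, PFS at 6 months |
| 9 | 0 | the above and PFS at 3 months |

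This step needs no model of response times.

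**4. Effect on confirmed ORR (illustration; the assumptions are mine).** 180 platinum eligible subjects enter uniformly over 13 months. Time to response is exponential with median m = 2, 3 or 4 months, the range that Protocol 3.2.1 gives for other tumor types. Confirmation takes a further 6 weeks (1.4 months). A subject with follow-up t > 1.4 has been captured as an eventual responder with probability 1 − 2^(−(t − 1.4)/m), averaged over t from 9 − L to 22 − L. The number with under 9 months of follow-up is 180 × L/13. The last column multiplies the captured share by a true ORR of 30%, one of the rows of Table 8.1-1.

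| L | Under 9 months | Captured, m = 2 / 3 / 4 | True 30% reads as |
|---|---|---|---|
| 0 | 0 | 98.4 / 94.5 / 89.4% | 29.5 / 28.4 / 26.8% |
| 3 | 42 | 95.5 / 89.1 / 82.1% | 28.7 / 26.7 / 24.6% |
| 6 | 83 | 87.4 / 78.1 / 69.9% | 26.2 / 23.4 / 21.0% |

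Relative to L = 0, a 3-month lag costs 0.9, 1.6 or 2.2 ORR points, and a 6-month lag about 3 to 6. For scale, the exact 95% CI at 30% with N=120 is 22.0% to 39.0%.

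**5. A second set of assumptions.** Put confirmations at weeks 12, 18, 24, 30 and 36 with weights 0.50/0.25/0.15/0.07/0.03 (early) or 0.35/0.25/0.20/0.12/0.08 (late), platinum eligible accrual uniform over 13 + L months, and the cutoff at month 22. Captured shares (early/late) are 99.2/98.2% at L = 3 and 94.2/91.2% at L = 6. At L = 3 the cost on a true 30% is 0.30 × 0.008 = 0.2 to 0.30 × 0.018 = 0.5 points. Setting the cutoff at month 22 gives the 13 months to the refractory cohort, which Section 3.2 does not do.

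**The case against.** The strongest reply is that the two rules need not collide. The 9-month rules in 8.3.1 and 8.3.2 are minimums, so one joint analysis at least 9 months after the later cohort fills would satisfy both of those sections and the 5.4.2 sentence. That stands, and a reader who infers that both rules can hold only if the cohorts close together goes too far. But nothing requires a joint analysis, it would delay the primary result, and it strains the word 'when' in Section 3.2.

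A second reply is that timing is settled where it is specified: 8.3.2 in the statistical section, supported by 3.2, the Synopsis design text and SAP 2.1. Section 8.3.2 also says final, and 5.4.2 does not. This is a good reason to expect Rule B to be followed. It does not remove an unqualified contrary sentence that appears twice.

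A third reply is that the consequence is limited. SAP Section 5 tests only the primary endpoint, so platinum eligible ORR is estimated and not tested. The SAP already withholds landmark rates when follow-up is short, and it reports minimum follow-up. That stands, and it limits the weight of the point.

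A reader might also infer from Amendment 05, which enlarged the platinum eligible cohort, that this cohort closes later. The documents do not show which cohort closes first.

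**Conclusion.** The contradiction is real, but the harm is conditional. It needs platinum eligible to close later, the 5.4.2 and Synopsis sentence to be followed, and the analysis to run at the earliest permitted date. Minimum follow-up is then 9 − L months. Any L above 0 loses the 9-month OS rate in that cohort, L above 3 also loses the 6-month PFS and OS rates, and confirmed ORR is understated.

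The ORR loss is small up to a lag of about 3 months, between 0.2 and 2.2 points on a true 30% across the two sets of assumptions. Losses at longer lags are illustrations only, since they rest on assumed lags, accrual and response times. It would be wrong to conclude that platinum eligible ORR will be biased: nothing is lost if that cohort closes first or at the same time, or if the analysis waits for the later cohort. The primary comparison, its alpha and its power are untouched. The wording should still be corrected, because one of two written rules can bias a secondary estimate and the plan does not say which one governs.

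**What to change.** 1. In Protocol 5.4.2 and the Synopsis (Secondary Endpoints), replace the sentence with the rule in 8.3.2: within each cohort, ORR, DOR, PFS and OS are analysed at least 9 months after that cohort's planned number (about 180 or 216) has been randomized. Keeping the 8.3.2 trigger avoids adding another one.
2. State that all pooled analyses wait until both cohorts have reached that point. This should cover PFS and OS, and also ORR and DOR by PD-L1, HPV p-16 and TMB, which would otherwise have no timing rule once the sentence is removed.
3. Reconcile SAP 2.1 with the protocol. It already uses a clock for each cohort, so what remains there is the 6 months against the protocol's 9.

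The cost is wording in two protocol places and the SAP, with no change to sample size, alpha or the primary analysis. The downside is that platinum eligible and pooled results may come after the primary result.

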## 6. ADVERSE EVENTS

An *Adverse Event (AE)* is defined as any new untoward medical occurrence or worsening of a preexisting medical condition in a clinical investigation subject administered study drug and that does not necessarily have a causal relationship with this treatment. An AE can therefore be any unfavorable and unintended sign (such as an abnormal laboratory finding), symptom, or disease temporally associated with the use of study drug, whether or not considered related to the study drug.

The causal relationship to study drug is determined by a physician and should be used to assess all AE. The causal relationship can be one of the following:

Related: There is a reasonable causal relationship between study drug administration and the AE.

Not related: There is not a reasonable causal relationship between study drug administration and the AE.

The term “reasonable causal relationship” means there is evidence to suggest a causal relationship.

Adverse events can be spontaneously reported or elicited during open-ended questioning, examination, or evaluation of a subject. Care should be taken not to introduce bias when collecting

AEs and/or SAEs. Inquiry about specific AEs should be guided by clinical judgement in the context of known adverse events, when appropriate for the program or protocol.

Sponsor or designee will be reporting adverse events to regulatory authorities and ethics committees according to local applicable laws including European Directive 2001/20/EC and FDA Code of Federal Regulations 21 CFR Parts 312 and 320.

## 6.1 Serious Adverse Events

A *Serious Adverse Event (SAE)* is any untoward medical occurrence that at any dose:

- results in death
- is life-threatening (defined as an event in which the subject was at risk of death at the time of the event; it does not refer to an event which hypothetically might have caused death if it were more severe)
- requires inpatient hospitalization or causes prolongation of existing hospitalization (see **NOTE** below)
- results in persistent or significant disability/incapacity
- is a congenital anomaly/birth defect
- is an important medical event (defined as a medical event(s) that may not be immediately life-threatening or result in death or hospitalization but, based upon appropriate medical and scientific judgment, may jeopardize the subject or may require intervention [eg, medical, surgical] to prevent one of the other serious outcomes listed in the definition above.) Examples of such events include, but are not limited to, intensive treatment in an emergency room or at home for allergic bronchospasm; blood dyscrasias or convulsions that do not result in hospitalization.) Potential drug induced liver injury (DILI) is also considered an important medical event. (See [Section 6.6](#) for the definition of potential DILI.)

Suspected transmission of an infectious agent (eg, pathogenic or nonpathogenic) via the study drug is an SAE.

Although pregnancy, overdose, cancer, and potential drug induced liver injury (DILI) are not always serious by regulatory definition, these events must be handled as SAEs. (See [Section 6.1.1](#) for reporting pregnancies).

Any component of a study endpoint that is considered related to study therapy (eg, death is an endpoint, if death occurred due to anaphylaxis, anaphylaxis must be reported) should be reported as SAE (see [Section 6.1.1](#) for reporting details).

### NOTE:

The following hospitalizations are not considered SAEs in BMS clinical studies:

- a visit to the emergency room or other hospital department < 24 hours, that does not result in admission (unless considered an important medical or life-threatening event)
- elective surgery, planned prior to signing consent
- admissions as per protocol for a planned medical/surgical procedure
- routine health assessment requiring admission for baseline/trending of health status (eg, routine colonoscopy)

- medical/surgical admission other than to remedy ill health and planned prior to entry into the study. Appropriate documentation is required in these cases
- admission encountered for another life circumstance that carries no bearing on health status and requires no medical/surgical intervention (eg, lack of housing, economic inadequacy, caregiver respite, family circumstances, administrative reason)
- Admission for administration of anticancer therapy in the absence of any other SAEs (applies to oncology protocols)

### **6.1.1 Serious Adverse Event Collection and Reporting**

Sections 5.6.1 and 5.6.2 in the Investigator Brochure (IB) represent the Reference Safety Information to determine expectedness of serious adverse events for expedited reporting. Following the subject's written consent to participate in the study, all SAEs, whether related or not related to study drug, must be collected, including those thought to be associated with protocol-specified procedures.

All SAEs must be collected that occur during the screening period and within 100 days of discontinuation of dosing, except in cases where a study participant has started a new anti-neoplastic therapy. However, any SAE occurring after the start of a new treatment that is suspected to be related to study treatment by the investigator will be reported. If applicable, SAEs must be collected that relate to any later protocol specified procedure (eg, a follow-up skin biopsy). For subjects randomized/assigned to treatment and never treated with study drug, SAEs should be collected for 30 days from the date of randomization/treatment assignment. The investigator must report any SAE that occurs after these time periods and that is believed to be related to study drug or protocol-specified procedure.

An SAE report must be completed for any event where doubt exists regarding its seriousness.

If the investigator believes that an SAE is not related to study drug, but is potentially related to the conditions of the study (such as withdrawal of previous therapy or a complication of a study procedure), the relationship must be specified in the narrative section of the SAE Report Form.

SAEs, whether related or not related to study drug, and pregnancies must be reported to Sponsor or designee within 24 hours of awareness of the event. SAEs must be recorded on the SAE Report Form; pregnancies on a Pregnancy Surveillance Form (electronic or paper forms). The preferred method for SAE data reporting collection is through the eCRF. The paper SAE/pregnancy surveillance forms are only intended as a back-up option when the eCRF system is not functioning. In this case, the paper forms are to be transmitted via email or confirmed facsimile (fax) transmission to:

**SAE Email Address:** Refer to Contact Information list.

**SAE Facsimile Number:** Refer to Contact Information list.

For studies capturing SAEs through electronic data capture (EDC), electronic submission is the required method for reporting. In the event the electronic system is unavailable for transmission,

paper forms must be used and submitted immediately. When paper forms are used, the original paper forms are to remain on site.

**SAE Telephone Contact** (required for SAE and pregnancy reporting): Refer to Contact Information list.

If only limited information is initially available, follow-up reports are required. (Note: Follow-up SAE reports must include the same investigator term(s) initially reported.)

If an ongoing SAE changes in its intensity or relationship to study drug or if new information becomes available, the SAE report must be updated and submitted within 24 hours to Sponsor or designee using the same procedure used for transmitting the initial SAE report.

All SAEs must be followed to resolution or stabilization.

BMS will be reporting adverse events to regulatory authorities and ethics committees according to local applicable laws including European Directive 2001/20/EC and FDA Code of Federal Regulations 21 CFR Parts 312 and 320. A SUSAR (Suspected, Unexpected Serious Adverse Reaction) is a subset of SAEs and will be reported to the appropriate regulatory authorities and investigators following local and global guidelines and requirements.

